22.0 Withdrawal of Subjects*

N/A: This study is not enrolling subjects. This section does not apply.

22.1 Describe anticipated circumstances under which subjects may be withdrawn from the research without their consent.

Participants may be withdrawn from the research without their consent if the PI or research team member discovers a participant is in severe psychological distress or is admitted into the hospital for a psychiatric condition.

22.2 Describe any procedures for orderly termination.

NOTE: Examples may include return of study drug, exit interview with clinician. Include whether additional follow up is recommended for safety reasons for physical or emotional health.

NOT APPLICABLE

22.3 Describe procedures that will be followed when subjects withdraw from the research, including retention of already collected data, and partial withdrawal from procedures with continued data collection, as applicable.

We will attempt to use all the available data obtained from all participants (intention to treat). Pre and post comparison of the experimental Group will be conducted as aggregate means using all available data collected.

When participants decide to leave the study, we will ask them if they would allow us to use the data we have collected before their decision to withdraw. If the subjects agree to use the data, the collected data will be handled and analyzed the same as research data. If the participants do not allow the use of the data, we will make every attempt to destroy the data.

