19.0 Data Management and Analysis*

19.1 Describe the data analysis plan, including any statistical procedures. This section applies to both quantitative and qualitative analysis.

As a pilot study, power analysis is not necessary. Statistical analysis will include descriptive statistics, mixed-effect modeling for repeated measures, and within-group and between-groups comparisons using t-tests or Wilcoxon signed-rank test as appropriate and Cohen's d effect size calculation. Multi-time data collection will be done via daily mobile-APP use.

We will follow the standard procedure in quantitative data analysis that includes general data inspection to verify the accuracy, completeness, and normality of the dataset using the SPSS23 program. We will compare clinical outcomes within-group (pre-post) as well as between groups in the post-intervention period. We will follow the recommendation of inappropriate statistical analysis and interpretation specific to each survey. For continuous variables, we will use a paired student t-test, independent t-test analytical approaches. For categorical variables and non-normally distributed variables, we will use non-parametric statistical methods (X2). Frequency distributions will be produced for all variables, and demographic information will be used to describe the sample. The impact of the M-App use on outcome variables will be analyzed using paired t-test and repeated measure ANOVA.

Qualitative data (focused-group interview data) will be analyzed using the standard qualitative thematic analysis procedure. We will transcribe the audio-recorded data and upload it into NViVo data management system. We will adhere to the thematic analysis method, described as follows:

1. A researcher will read and re-read the entire text to get a general sense of the participants' whole experience of being a student during the COVID-19 pandemic. While reading through the transcript, the researcher will take initial notes and perform a general review to get familiar with the data before analyzing the data.
2. The researcher will descriptively open code by dividing the significant text segments into 'meaningful units', keeping the participants' own words. The researcher will re-read all the codes again to eliminate redundancies.

The comparative discussion of these codes with other research team members to achieve a consensus will provide a validation step.

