There is a potential risk of emotional distress to participants when answering survey questions about symptoms or feelings. Although unlikely, participants may experience sensations of anxiety, depression, and worse physical symptoms. Participants will be instructed to rest and re-focus their attention from completing the survey in such a scenario. Suppose a participant expresses any distress, or the research team suspects the participant is experiencing distress for any reason during the research. In that case, the participant may be removed from the study and offered a referral to mental health services. The adverse events will be reported to the IRB by the PI within the required timeframe.

21.4 Describe how the safety information will be collected (e.g., with case report forms, at study visits, by telephone calls with participants).

The PI will collect safety data during telephone calls with the participant(s) and during data collection from the participant's self-evaluations.

21.5 Describe the frequency of safety data collection.

Safety data collection occurs once every two weeks for eight weeks and one hour during the focus group interview.

21.6 Describe who will review the safety data.

The PI and research team will review the safety data.

21.7 Describe the frequency or periodicity of review of cumulative safety data.

The review of cumulative safety data will occur weekly.

21.8 Describe the statistical tests for analyzing the safety data to determine whether harm is occurring.

We will use descriptive statistics (counts of the event) to determine the events of distress.

21.9 Describe any conditions that trigger an immediate suspension of the research.

We do not anticipate any situation that would trigger an immediate suspension of the study.

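### Section 22.3 describes the experimental group's pre-post comparison as aggregate means over all available data, section 19.1 names within-person methods, and nothing says which governs when people leave

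*Combined protocol and SAP*

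**What the plan says.** Section 22.3 is the only place that says how data from people who withdraw enter the analysis. It commits to using whatever data are available from everyone, and adds: "Pre and post comparison of the experimental Group will be conducted as aggregate means using all available data collected". On voluntary withdrawal it says: "When participants decide to leave the study, we will ask them if they would allow us to use the data". Data released in this way are analysed with the rest. Where permission is refused, the team tries to destroy the data, so that person appears in neither mean.

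The prompt for 22.3 also asks about "partial withdrawal from procedures with continued data collection, as applicable". The answer does not say whether someone who stops practising is still asked for the final questionnaires.

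Section 19.1, the data analysis plan, says: "We will compare clinical outcomes within-group (pre-post) as well as between groups in the post-intervention period". It continues: "For continuous variables, we will use a paired student t-test, independent t-test analytical approaches". It also lists mixed-effect modelling for repeated measures, the Wilcoxon signed-rank test, repeated-measures ANOVA and Cohen's d. It gives no rule for a missing post score and does not refer to 22.3. Section 19.3 has the coordinator contact participants about missing entries, but does not say that this reaches people who have left.

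**The concern.** A comparison of two group means is a clean measure of change only if the same people are in both. Under the literal 22.3 rule, the pre mean includes leavers who released their data and the post mean does not. The apparent change then mixes real change with a shift in who is being measured. If leavers had worse baseline scores, the group seems to improve although nobody did. If they had better scores, real improvement is partly hidden.

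PAHSS symptom severity and EmPHasis-10 quality of life are the endpoints named in section 3.1. Section 19.1 plans Cohen's d, so a shift of this kind could carry into the pilot's reported effect sizes.

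**Working it through.** **Inputs.** Attrition is 20% in section 5.1 and 15% in section 7.3. Section 5.1 enrols 20 and plans 8 to 10 per group. Table 1 schedules PAHSS and EmPHasis-10 at the start, in the fourth week and in the eighth week. The documents give no SD, no pre-post correlation and no leaver-stayer difference, so these are assumed below.

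**The plan's own figure.** To keep 16: 16/(1 − 0.20) = 20; 16/(1 − 0.15) = 18.8, rounded up to 19. Enrolling 20 fits both rates. With 10 in the group, 20% attrition means 2 leavers.

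**The extra term.** Let f be the share with a pre score but no post score, and D the leavers' baseline mean minus the stayers'.

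- Pre mean over everyone = stayers' pre mean + f × D.
- Post mean = stayers' post mean.
- Aggregate change = stayers' paired change − f × D.

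Example: 8 stayers with mean 0, 2 leavers with mean 1 SD, nobody changes. The pre mean is (8×0 + 2×1)/10 = 0.20, the post mean is 0, and the apparent change is −0.20 SD (higher is worse, so this looks like improvement).

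| Assumed D | f = 0.15 | f = 0.20 |
|---|---|---|
| 0 | 0 | 0 |
| 0.5 SD | 0.075 | 0.10 |
| 1 SD | 0.15 | 0.20 |

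A negative D gives the same sizes with the sign reversed.

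**Precision** (10 pre scores, 8 post scores, random dropout, correlation r, unit SD).

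- Paired SE = √(2(1 − r)/8): 0.27 at r = 0.7, 0.35 at 0.5, 0.42 at 0.3.
- Aggregate SE = √(1/10 + 1/8 − 2r×8/80): 0.29, 0.35, 0.41.
- Mixed model, by simulation: 0.27, 0.34, 0.40.

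**Comparison of methods.** Simulation: 10 people, 2 leave, three visits, equal correlation between visits, no true change, higher = worse. The mixed model is REML with a random participant intercept and visit as a factor. Entries are mean bias in SD; repeat runs agreed to within about 0.02.

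| Assumed r | Who leaves | Aggregate | Paired | Mixed |
|---|---|---|---|---|
| 0.7 | Random | 0.00 | 0.00 | 0.00 |
| 0.7 | 2 worst baselines | −0.23 | +0.09 | −0.02 |
| 0.7 | 2 worst week-4 scores, score lost | −0.21 | +0.01 | −0.07 |
| 0.7 | 2 worst week-4 scores, score kept | −0.22 | 0.00 | 0.00 |
| 0.7 | 2 worst unseen post scores | −0.32 | −0.10 | −0.17 |
| 0.5 | 2 worst baselines | −0.16 | +0.16 | about 0 |
| 0.5 | 2 worst unseen post scores | −0.32 | −0.16 | −0.25 |
| 0.3 | 2 worst baselines | −0.11 | +0.21 | −0.01 |

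The non-random rows are deliberately extreme: the worst-baseline rule implies a gap of 1.6 SD, beyond the 0.5 to 1 SD used above. The identity still holds: at r = 0.7, +0.09 − 0.20×1.6 = −0.23. A softer rule (score plus equal noise) at r = 0.7 gives aggregate biases of −0.15 to −0.22.

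The mixed model was less biased than aggregate means in every non-random case. Paired change was not: with baseline-driven dropout it ties at r = 0.5 and is about twice as far off at r = 0.3, against the intervention. When an unseen later score drives dropout, paired change is the less biased of the two within-person methods.

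**The case against.** The strongest reply is that 22.3 answers an ethics-board prompt about withdrawal and data retention, while 19.1 is the analysis plan. A paired test cannot count anyone in one mean only, and a mixed model is an ordinary way to use all available data. On that reading 22.3 concerns retention and group-level reporting, and 19.1 governs. This reading is open and largely stands: the documents do not establish that the team will subtract unmatched means. What remains is that 22.3 states a method, 19.1 gives no rule for a missing post score, and an analyst facing dropout would naturally look in the withdrawal section.

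A reader might also infer that sicker participants will leave, so false improvement is to be expected. The documents do not support that. Section 21.3 calls worsening symptoms or distress from the surveys unlikely, and both removal clauses are permissive: "the participant may be removed from the study and offered a referral to mental health services" in 21.3, and "Participants may be withdrawn from the research without their consent" in 22.1. Symptom-related dropout is possible, not shown.

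Nor is all of Aim 2 at risk. The between-group comparison in 19.1 is made in the post-intervention period and uses no pre mean. The short-term ratings are taken before and after each module use, so study dropout does not create this imbalance there. The Aim 1 feasibility and acceptability targets are untouched.

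Finally, the effect is small beside the sampling error of about 10 people per group. That is true, and it limits the weight of the point. It does not justify leaving the method unsettled when the remedy is a change of wording.

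**Conclusion.** The point holds as an unresolved conflict between 22.3 and 19.1, with a bias that follows if 22.3 is applied literally. The bias needs a leaver who permits data use, has a baseline score, has no post score, and differs from stayers at baseline. Someone who stops practising but still completes the final questionnaires counts in both means and adds nothing to it.

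For the assumed gaps of 0.5 to 1 SD and the planned attrition, the term is about 0.08 to 0.20 SD, less than one standard error. Only the most extreme simulated dropout exceeds one standard error (−0.32 SD against about 0.27 at r = 0.7). The direction cannot be predicted from the documents, and the gaps and correlations are assumptions throughout. The point is worth correcting because the two named endpoints are affected and the better method is already in the plan.

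**What to change.** Replace the aggregate-means sentence in 22.3 with a reference to 19.1. In 19.1, state that pre-post change in the experimental group is estimated primarily by the repeated-measures mixed model already named there: baseline, week 4 and week 8, a random participant intercept, and every participant with any usable outcome data. State its assumption, that dropout depends only on observed scores. Give the paired change in participants with both scores as supportive. Report how many left, with the available baseline scores of leavers and stayers.

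The cost is wording in two sections and slightly more analysis, with no meaningful loss of precision in the checks above. The two results may differ and would need explaining. The missing-data assumption cannot be tested, and the mixed model is still biased if an unseen later score drives dropout. Section 11.1 says enrolment has ended and section 21.2 has the team reviewing clinical outcomes, so the choice of primary method may not be blind to results. It should be dated and recorded as such.

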23.0 Risks to Subjects*

23.1 List the reasonably foreseeable risks, discomforts, hazards, or inconveniences to the subjects related to their participation in the research. Consider physical, psychological, social, legal, and economic risks. Include a description of the probability, magnitude, duration, and reversibility of the risks.

NOTE: Breach of confidentiality is always a risk for identifiable subject data.

There are no foreseeable physical risks, discomfort, hazard, or inconveniences to the subjects related to their participation in this research. However, there is potential physical harm if participants use the M-App in circumstances that require total attention, such as driving or operating heavy machinery. There is an inherent risk of participants becoming so relaxed and drift off into a sleep state, which may put them in danger during these activities. Therefore, we will instruct participants in the proper use of the M-App and the environment/conditions they need to avoid practicing with the M-App.

For a Zoom intervention group, there is always the chance that someone will share something someone else said (confidentiality breach). At the beginning of the interview, we will remind participants not to share this information with anyone. (This information will be a part of the consent document, indicating no guarantee that this may not occur).

There is a potential risk of emotional discomfort to participants when answering survey questions about symptoms or feelings. Although unlikely, participants may experience sensations of anxiety, depression, and worse physical symptoms. Participants will be instructed to rest and re-focus their attention from completing the survey in such a scenario. If needed, participants will be given the contact information in their local areas (according to their primary care doctors). Questionnaires included in this research study are standardized tools used widely with no reported adverse harm. Fatigue is possible when answering questions from a battery of questionnaires. However, most surveys used in this study are shortened versions that generally require less than 10 minutes to complete.

23.2 Describe procedures performed to lessen the probability or magnitude of risks, including procedures being performed to monitor subjects for safety.

To address potential physical harm (mentioned above), we will provide specific instructions on how to complete the M-App modules at home.

To monitor subjects for safety risk, we will conduct weekly research meetings to review the progress of the research activity and any participants' safety concerns. We will create action plans to mitigate any issues that may arise.

We will employ all reasonable efforts to protect the confidentiality of the participants' protected health information. Identifiable data is immediately de-identified, and de-identified data is stored separately from identifiable data. We will keep participants' names and other identifying information confidential when the data is prepared or oral or written publications.

Specific to participants' interviews, there is a potential risk of emotional distress due to the sensitive nature of the topics. We will provide all interviewed participants with information on mental health resources and support groups at the time of enrollment.

23.3 *If applicable, indicate which procedures may have risks to the subjects that are currently unforeseeable.*

None other than the potentiality of "falling asleep" during the practice.

23.4 *If applicable, indicate which research procedures may have risks to an embryo or fetus should the subject be or become pregnant.*

Response:

NONE

23.5 *If applicable, describe risks to others who are not subjects.*

Response:

NONE

24.0 Potential Benefits to Subjects*

24.1 *Describe the potential benefits that individual subjects may experience by taking part in the research. Include the probability, magnitude, and duration of the potential benefits. Indicate if there is no direct benefit.*

NOTE: Compensation **cannot** be stated as a benefit.

There are potential benefits that individual subjects may experience by taking part in the research. Based on existing literature reporting on the use of M-App, mindfulness practice can increase one's level of Mindfulness that may help with focus and attention beneficial to their mental health and well-being. Participation in this study may benefit from stress and anxiety reduction, which can be helpful to their academic learning and social interaction.

25.0 Compensation for Research-Related Injury

N/A: The research procedures for this study do not present risk of research related injury (e.g. survey studies, records review studies). This section does not apply.

25.1 *If the research procedures carry a risk of research related injury, describe the available compensation to subjects in the event that such injury should occur.*

NOT APPLICABLE

25.2 *Provide a copy of contract language, if any, relevant to compensation for research related injury.*

NOTE: *If the contract is not yet approved at the time of this submission, submit the current version here. If the contract is later approved with different language regarding research related injury, you must modify your response here and submit an amendment to the IRB for review and approval.*

NOT APPLICABLE

26.0 Economic Burden to Subjects

26.1 *Describe any costs that subjects may be responsible for because of participation in the research.*

NOTE: Some examples include transportation or parking.

The only anticipated cost to participants relevant to the study includes data charges from their phone carrier if they are not using a Wi-Fi service or go over the allotted data usage with their phone carrier.

N/A: This study is not enrolling subjects, or is limited to records review procedures only. This section does not apply.

27.0 Compensation for Participation

27.1 *Describe the amount and timing of any compensation to subjects, including monetary, course credit, or gift card compensation.*

Participants will be compensated at four timepoints with US Bank Prepaid Cards, in a total value up to \$90.00 after completing the study.

N/A: This study is not enrolling subjects, or is limited to records review procedures only. This section does not apply.

N/A: There is no compensation for participation. This section does not apply.

28.0 Consent Process

28.1 *Indicate whether you will be obtaining consent.*

NOTE: This does not refer to consent documentation, but rather whether you will be obtaining permission from subjects to participate in a research study. Consent documentation is addressed in Section 29.0.

Yes *(If yes, Provide responses to each question in this Section)*

No *(If no, Skip to Section 29.0)*

28.2 *Describe where the consent process will take place. Include steps to maximize subjects' privacy.*

Once it is determined a participant is qualified, they will have access to a written version of the consent form that the IRB has approved. We will email a copy of the consent form to review at least two days before providing consent. They will gain a further, detailed understanding of the study, participation requirement, and other general information about the human research subject in the privacy of their homes. The consent process will take place during a virtual meeting between a member of the research team and the interested, eligible participant to review the content of the consent form. The research coordinator will put the consent form

up on the screen and go through it and then ask the participant to either orally agree or not. If they don't consent, they may leave by logging out. If they stay, they are verbally demonstrating their consent. During this meeting, we will provide the participant with plenty of opportunities to ask additional questions about the study. If it is agreeable with the participant, the researcher will obtain verbal consent.

28.3 Describe how you will ensure that subjects are provided with a sufficient period of time to consider taking part in the research study.

NOTE: It is always a requirement that a prospective subject is given sufficient time to have their questions answered and consider their participation. See "SOP: Informed Consent Process for Research (HRP-090)" Sections 5.5 and 5.6.

The participant will receive a written consent form at least two days before the virtual meeting between the eligible participant and the research coordinator. The participant will have sufficient time to ask further questions about the study during the meeting. If they are unsure whether to participate at that time, they will be given an additional day to decide their participation. In such a case, the research coordinator can schedule another virtual meeting convenient for the participant.

28.4 Describe any process to ensure ongoing consent, defined as a subject's willingness to continue participation for the duration of the research study.

Emails will be sent to the participants each week by the research team to remind participants of their volunteer status and ability to withdraw from participation at any time.

28.5 Indicate whether you will be following "SOP: Informed Consent Process for Research (HRP-090)." Pay particular attention to Sections 5.4-5.9. If not, or if there are any exceptions or additional details to what is covered in the SOP, describe:

- *The role of the individuals listed in the application who are involved in the consent process*
- *The time that will be devoted to the consent discussion*
- *Steps that will be taken to minimize the possibility of coercion or undue influence*
- *Steps that will be taken to ensure the subjects' understanding*

We will be following HRP-900 with the exception that consent provisions will not be made to conduct consent in languages other than English even if this is preferred by the participant because we expect that the participants will speak English sufficiently to understand the consent form.

We have reviewed and will be following "SOP: Informed Consent Process for Research (HRP-090)."

Non-English Speaking Subjects

N/A: This study will not enroll Non-English speaking subjects.
(*Skip to Section 28.8*)

28.6 *Indicate which language(s) other than English are likely to be spoken/understood by your prospective study population or their legally authorized representatives.*

NOTE: The response to this Section should correspond with your response to Section 8.4 of this protocol.

Response:

NOT APPLICABLE

28.7 *If subjects who do not speak English will be enrolled, describe the process to ensure that the oral and written information provided to those subjects will be in that language, how you will ensure that subjects are provided with a sufficient period of time to consider taking part in the research study, and any process to ensure ongoing consent. Indicate the language that will be used by those obtaining consent.*

NOTE: Guidance is provided on "SOP: Informed Consent Process for Research (HRP-090)."

Response:

NOT APPLICABLE

Cognitively Impaired Adults

N/A: This study will not enroll cognitively impaired adults.
(*Skip to Section 28.9*)

28.8 *Describe the process to determine whether an individual is capable of consent.*

Response: NOT APPLICABLE

Adults Unable to Consent

N/A: This study will not enroll adults unable to consent.
(*Skip to Section 28.13*)

When a person is not capable of consent due to cognitive impairment, a legally authorized representative should be used to provide consent (Sections 28.9 and 28.10) and, where possible, assent of the individual should also be solicited (Sections 28.11 and 28.12).

28.9 *Describe how you will identify a Legally Authorized Representative (LAR). Indicate that you have reviewed the "SOP: Legally Authorized Representatives, Children, and Guardians (HRP-013)" for research in New York State.*

NOTE: Examples of acceptable response includes: verifying the electronic medical record to determine if an LAR is recorded.

Response: NOT APPLICABLE

We have reviewed and will be following "SOP: Legally Authorized Representatives, Children, and Guardians (HRP-013)."

28.10 *For research conducted outside of New York State, provide information that describes which individuals are authorized under applicable law to consent on behalf of a prospective subject to their participation in the research. One method of obtaining this information is to have a legal counsel or authority review your protocol along with the definition of "legally authorized representative" in "SOP: Legally Authorized Representatives, Children, and Guardians (HRP-013)."*

Response: NOT APPLICABLE

28.11 *Describe the process for assent of the adults:*

- *Indicate whether assent will be obtained from all, some, or none of the subjects. If some, indicate which adults will be required to assent and which will not.*

Response: NOT APPLICABLE

- *If assent will not be obtained from some or all subjects, provide an explanation of why not.*

Response: NOT APPLICABLE

28.12 *Describe whether assent of the adult subjects will be documented and the process to document assent.*

NOTE: The IRB allows the person obtaining assent to document assent on the consent document using the "Template Consent Document (HRP-502)" Signature Block for Assent of Adults who are Legally Unable to Consent.

Response: NOT APPLICABLE

Subjects who are not yet Adults (Infants, Children, and Teenagers)

N/A: This study will not enroll subjects who are not yet adults.
(*Skip to Section 29.0*)

28.13 *Describe the criteria that will be used to determine whether a prospective subject has not attained the legal age for consent to treatments or procedures involved in the research under the applicable law of the jurisdiction in which the research will be conducted (e.g., individuals under the age of 18 years). For research conducted in NYS, review "SOP: Legally Authorized Representatives, Children, and Guardians (HRP-013)" to be aware of which individuals in the state meet the definition of "children."*

NOTE: Examples of acceptable responses include: verification via electronic medical record, driver's license or state-issued ID, screening questionnaire.

Response: **NOT APPLICABLE**

28.14 *For research conducted outside of New York State, provide information that describes which persons have not attained the legal age for consent to treatments or procedures involved in the research, under the applicable law of the jurisdiction in which research will be conducted. One method of obtaining this information is to have a legal counsel or authority review your protocol along the definition of "children" in "SOP: Legally Authorized Representatives, Children, and Guardians (HRP-013)."*

Response: **NOT APPLICABLE**

28.15 *Describe whether parental permission will be obtained from:*

Response:

- One parent even if the other parent is alive, known, competent, reasonably available, and shares legal responsibility for the care and custody of the child.
- Both parents unless one parent is deceased, unknown, incompetent, or not reasonably available, or when only one parent has legal responsibility for the care and custody of the child.
- Parent permission will not be obtained. A waiver of parent permission is being requested.

NOTE: The requirement for parent permission is a protocol-specific determination made by the IRB based on the risk level of the research. For guidance, review the "CHECKLIST: Children (HRP-416)."

28.16 *Describe whether permission will be obtained from individuals other than parents, and if so, who will be allowed to provide permission. Describe your procedure for determining an individual's authority to consent to the child's general medical care.*

Response: NOT APPLICABLE

28.17 Indicate whether assent will be obtained from all, some, or none of the children. If assent will be obtained from some children, indicate which children will be required to assent.

Response: NOT APPLICABLE

28.18 When assent of children is obtained, describe how it will be documented.

Response: NOT APPLICABLE

